**Maximal aerobic power (VO2 max).** The measurement of VO2max (or peak) will be used to formulate the prescription for CEx at the screening visit. Increases in VO2max in response to exercise training will also verify that the exercise was of sufficient intensity to induce cardiorespiratory adaptations. During an initial 5-min warm-up, walking speed will be adjusted to elicit a HR that is ~70% of maximal HR (from the screening GXT). Speed will then be held constant and the grade of the treadmill will be increased by 2% every 2 minutes until volitional exhaustion or until the test is stopped (see section 4.1.2b). The O2 and CO2 content of expired air will be measured continuously by open circuit spirometry and averaged every 30 sec using an automated online system (TrueMax 2400; ParvoMedics, Sandy, UT). Objective evidence that VO2max has been attained will include at least 2 of the following: a plateau in VO2 despite an increased energy demand, a respiratory exchange ratio in excess of 1.10, and a maximal HR within 10 beats of the age-predicted value. In the absence of these benchmarks, the maximum measured VO2 will be deemed VO2 peak.

**Muscle strength (1-RM).** Muscle strength will be evaluated as the 1-RM (the maximal weight that can be lifted only 1 time using correct lifting form through the full range of motion) for the upper and lower body REx performed during weeks 1-16. 1RMs will be measured at week 0 and every 4 weeks to week 20. The change in muscle strength from week 0 to 16 will be a secondary outcome measure.

**Exercise Intervention.** Participants will be assigned with equal probability to one of the two exercise intervention arms (high intensity interval training [HIIT] or continuous moderate intensity exercise [CME]) following completion of screening procedures. Randomization procedures will be site-specific, and use permuted blocks with stratification by sex and 10-year age categories (i.e., 50-59 years, 60-69 years, 70-80 years), to assure similar distribution in each arm. The allocation to study arm will remain blinded (masked) to the research assistant conducting the physical function assessments and to laboratory personnel.

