## F. Data Analysis Plan:

**Statistical Considerations.** We hypothesize that among older PWH, HIIT will lead to better physical function and reduced fatigue through improvements in mitochondrial bioenergetics compared with CME.

**Sample Size Calculations:** We assume a 1:1 randomization to HIIT or CME balanced by site, sex ( $\geq 25\%$  women) and age category (50-59, 60-69, and 70+) with a conservative 20% dropout rate, resulting in 40 evaluable participants/group. The second randomization at week 16 and will also be balanced by initial randomization (2x2 factorial design). Aim 1 and 2 power calculations assume two-sided, 2-sample/paired *t*-tests for between/within group comparisons of the change from baseline with a 0.05 significance level. We assume conservative within subject correlations ( $\rho$ ) of 0.7 or 0.5 to estimate the standard deviation (SD) of the outcome change, larger correlations and repeated measures will result in additional power. The Aim 1 primary outcome is change in 400-MWT. We assume an effect size comparable to Toohey, an intervention comparing HIIT to CME among middle-aged (mean age 51, SD 12 years) cancer survivors that resulted in a mean (SD) difference of 97 (82) and 36 (68) meters in 6-minute walk distance among HIIT and CME, respectively. Using  $\rho=0.7$ , and a sample size of 40/group, we will have  $>88\%$  power to detect a comparable *between* group differences of 45 (38) and 20 (38) second improvement in 400-MWT in HIIT and CME, respectively. For reference, in our prior exercise study, PWH had a 25 second improvement in 400-MWT. This also provides  $>99\%$  and  $>81\%$  power to detect *within* group differences in the HIIT and CME arms. For morning and evening fatigue, we assume a baseline mean of 19(8) and 27(8) points, respectively ([name], unpublished data). With  $\rho=0.5$ , and a sample size of 40/group, we will have  $>80\%$  to detect a change of  $\geq 27\%$  and  $\geq 20\%$ , respectively. The primary Aim 2 outcome is change in State 3 respiration. Based on Robinson, we estimate a baseline mean (SD) of 580 (180) pmol  $O_2$ /min/mL using  $\rho=0.5$ . This provides  $>81\%$  power to detect a difference in the change of 50% (HIIT) and 30% (CME). The muscle substudy is considered exploratory, however, we anticipate adequate power. Using preliminary data, combining HEALTH+ exercise groups (N=24), provides  $>80\%$  power to detect a change of -8.7% in MRI-PDFF of HEALTH+ participants. For within exercise group (CME or HIIT) comparisons, a sample size of 12 provides  $>80\%$  power to detect a difference of -12.5%. For the CME versus HIIT change from baseline comparison, a sample size of 12 per group provides  $>80\%$  power to detect group differences of 9.8%. For the change in OxPhos, combining HEALTH+ exercise groups (N=24, 3 dropouts/group), provides  $>80\%$  power to detect an OxPhos change of 0.039. For within exercise group (CME or HIIT) comparisons, a sample size of 12 provides  $>80\%$  power to detect an OxPhos difference of 0.055. For the CME versus HIIT change from baseline comparison, a sample size of 12 per group provides  $>80\%$  power to detect group OxPhos differences of 0.056. For the change in aim 3, combining HEALTH+ exercise groups, a sample size of N=24 (3 dropouts/ group), provides  $>80\%$  power to detect a 21%  $\dot{V}O_2$  change in HEALTH+ participants. For within exercise group (CME or HIIT) comparisons, a sample size of 12 provides  $>80\%$  power to detect 33% change in  $\dot{V}O_2$ . For the CME versus HIIT change from baseline comparison, a sample size of 12 per group provides  $>80\%$  power to detect a 30% difference in the 16-week change from baseline.

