will examine potential group (and site) differences in demographics and health and baseline measures with two-sample t test (or Wilcoxon), ANOVA (or Kruskal-Wallis test) or Chi-square test where appropriate. Variables that differ by group will be adjusted in sensitivity analyses. We will conduct primary analyses under an intention-to-treat principle (all participants analyzed based on randomized conditions). The impact of any missing data will be mitigated by the use of mixed effects modeling with baseline covariates that are conceptually relevant and associated to consistency in data collection. In the presence of missing data, mixed effects models are fitted with all available data and provide unbiased estimates of model parameters, as long as the data are missing at random or conditionally at random (conditional on the covariates). If appropriate, we will employ imputation techniques. False discovery rate (FDR) will be used to justify multiple comparison. All tests will be two sided.

Our primary aim is to determine the efficacy of HIIT vs CME on improving cognitive function over time. In stage 1 (baseline to 4 months), a general linear mixed model with participant ID as random effect:  $\text{score} = \text{Group} + \text{Time} + \text{Group} \times \text{Time} + \text{Site}$  will be used first to examine whether there is a significant group difference, wherein the study site is controlled to adjust for potential site effects. The best model fit with Bayesian information criterion (BIC) will determine the variance-covariance structure in above model. The significant interaction term in above model indicates a significant difference between two trajectories/slopes, i.e., treatment effect. The group comparison on the mean changes will also be contrasted with t test for effect size. In stage 2 (4 to 7 months), a similar general linear mixed model will applied:  $\text{score} = \text{Group1 (HIIT vs CME)} + \text{Group2 (Coaching vs Control)} + \text{Group1} \times \text{Group2} + \text{Time} + \text{Group1} \times \text{Time} + \text{Group2} \times \text{Time} + \text{Group1} \times \text{Group2} \times \text{Time} + \text{Site}$ , where the time is from 4 to 7 months. The non-significant interaction terms will be removed from the final model. Given any potential group differences in demographics and health at baseline, a sensitivity analysis will be conducted including those unbalanced variables in above models.

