For exploratory analysis, sex-by-group interaction and/or race-by-group interaction will be included in above models to explore the potentially moderating effects, conducted according to the rigorous methods proposed by Hayes. Given significant treatment effects on cognitive function, a PATH analysis will be conducted to explore the potential mediation effects of biomarker changes on cognitive function. We will also examine whether changes in parent R01 outcomes (e.g., VO2, physical function, fatigue) mediate cognitive changes. The exploratory blood markers will be obtained at baseline, 4- and 12 months, while the MRI neuroimaging markers will be obtained at the UAB site at baseline and 4 months. The group difference of biomarkers will be evaluated using a similar linear mixed regression model:  $\text{scores} = \text{Group} + \text{Time} + \text{Group} \times \text{Time}$ , where the group difference on slopes and mean changes will be contrasted.

Our secondary aim is to examine psychological MoA of adherence to habitual PA at 12 months. We will examine distal predictors (i.e., sociodemographics, physical health, intervention type [HIIT vs CME and coaching vs control], changes in parent R01 outcomes [e.g., weight loss, physical function, fatigue] using laboratory and survey data, and proximal psychological predictors using EMA (e.g., self-efficacy, perceived benefits, motivation, social support). First, we will use a linear mixed regression with random intercept:  $\text{PA} = \text{Predictor} + \text{Time} + \text{Predictor} \times \text{Time} + \text{Site}$ , to examine the association between PA adherence and each of the predictors of interest, adjusting for study site. Secondly, we will conduct a multiple linear mixed regression with random intercept and all significant predictors detected above as fixed effects to examine the covariate-adjusted association between PA and predictors:  $\text{PA} = \text{Time} + \text{Predictor1} + \text{Predictor2} + \dots + \text{Site}$ . The time-by-predictor interactions will be evaluated and removed from the model if not significant. The variance-covariance structure (e.g., AR1) in above models will be determined by the best model fit measured by Bayesian information criterion (BIC).

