For EMA data, a linear mixed regression model including random effects for subject and day (within-subject) to account for the multilevel structure of the data will be used to examine the time-lagged effects of MoA variables occurring during a specified time interval (T-1) on PA during the subsequent (lagged) time interval (T) within each day of monitoring:  $\text{PA}(T) = \text{MoA}(T-1) + \text{Time of Day} + \text{Day} + \text{site} + \text{covariates}$ . The time interval T can be time of day or different days, for example we can use the MoA in Day 1 to predict the PA in Day 2 or use the MoA in the morning to predict the PA later in the same day. The covariates include significant distal predictors. Moderating effects will be explored by including interaction terms in above model. Concurrent effects of these MoA variables on PA (i.e., both the predictor and outcome were assessed during the same time interval) will also be examined. To explore whether the MoA variables mediate intervention (HIIT vs CME and coaching texting vs control) effects on PA, mediation analyses with focus on effect estimation rather than hypothesis testing will be conducted using path analysis with methods considering the multi-level nature of data and robust to non-normality (e.g., cluster bootstrapping), assuming a causal chain of the form: Intervention (HIIT vs CME) --> effect on MoA [as mediator] --> effect on PA. Using the estimated path coefficients, direct, indirect, and total effects will be estimated and uncertainty on these estimates be estimated computed in the form of confidence intervals. Using similar mediation approaches, we will also examine whether cognitive differences between groups at 12 months are mediated by differences in PA adherence at 12 months.

Quantitative feasibility, acceptability, and intervention fidelity outcomes will be compared across sites and exercise type using analysis of variance or chi-square tests when applicable.

Qualitative analysis will be conducted for acceptability questions at 4 months and PA barriers and facilitators at 12 months. [name] and [name] have a history of designing and analyzing data from qualitative studies. Content analysis will be used to derive themes related to barriers and facilitators to long-term PA, which will be synthesized with quantitative data to examine correlates (e.g., demographics, health).

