## STUDY TIMELINE

We propose a 5-year timeline to accomplish our specific aims (**Table 1**). By conducting a rigorous, prospective, randomized clinical trial testing two exercise regimens, we will overcome limitations of previous studies investigating non-pharmacological approaches to improving the *healthspan* of people living with HIV. This design enables us to characterize the clinical (i.e., physical function and patient-reported fatigue) and translational (i.e., mitochondrial bioenergetics) effects of these interventions in an understudied, yet growing, population. To ensure that we meet enrollment and data collection milestones, we anticipate 4.5 full years of research procedures, with the remaining 6 months to finalize data analyses and disseminate the final study results.

R01 Cognitive substudy (HEALTH-COG) will leverage newly enrolled participants at the two sites of the parent HEALTH study (R01AG066562), add a University of Alabama at Birmingham (UAB) site, add new measures (psychological mechanisms of adherence, cognitive function, biomarkers) and a 12 month follow-up. This study is optional (to UCD/UW participants) and open to anyone enrolled in the parent HEALTH study. The sub-study R01 proposes to enroll/randomize 110 participants (UAB=60, University of Washington (UW)/University of Colorado Denver (UCD)=50 total between the two sites). Based on current enrollment numbers at the parent study sites (UCD=37 and UW=31), we anticipate it will be feasible for the new R01 to enroll the remaining participants across both sites (~32 participants), and due to timing of funding in relation to enrollment at UCD and UW, approximately 8-10 additional participants at both UCD and UW will need to enroll to meet and overall goal of 110 in this sub-study. The parent study end date is ~2 years into new R01 (yielding 2-3 additional years of study).

| Table 1.               |     |                      |   |
|------------------------|-----|----------------------|---|
| Timing
(Year/Month) |     | Enrollment
Target | Milestones  |
| Year 1                 | JIT |                      | 
 
Protocol & Manual of procedures finalized
 
IRB approvals
 
Hospital/research center approvals
 
Data transfer agreements between UCD-AMC and UW finalized and executed
 
  |

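### The exploratory analysis of biomarker mediation runs only after a significant cognitive effect, a condition that mediation does not need and that would often fail at small to moderate effects

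*Combined protocol and SAP*

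**What the plan says.** Under Cognitive Substudy Statistical Analysis in section F (Data Analysis Plan), the exploratory paragraph states: "Given significant treatment effects on cognitive function, a PATH analysis will be conducted to explore the potential mediation effects", with biomarker changes as the mediators and cognition as the outcome. Nothing is planned for the case where the condition is not met.

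Three nearby statements set the context.

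- In the same paragraph, group differences in the biomarkers are to be estimated with a mixed model, with no condition attached. The sentence directly after the conditional one adds mediation by parent-trial outcomes (VO2, physical function, fatigue) and does not repeat the condition.
- For the psychological mechanisms of adherence, the EMA paragraph plans "mediation analyses with focus on effect estimation rather than hypothesis testing", reporting direct, indirect and total effects with confidence intervals. It also plans mediation of 12-month cognitive differences by physical activity, without a significance condition.
- On testing, the substudy text says "All tests will be two sided" and names the false discovery rate for multiplicity, but does not define the family of outcomes. Cognitive outcomes listed elsewhere include global and domain scores, subjective symptoms and diagnoses.

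On size, the Study Timeline says "The sub-study R01 proposes to enroll/randomize 110 participants", made up of 60 at UAB and 50 at the other two sites together.

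**The concern.** A significant total effect is not a prerequisite for mediation. The total effect is the sum of the indirect effect (treatment to marker, then marker to cognition) and the direct effect. Two things follow. The test of the total effect can have much less power than the tests of the two component paths. And with two active exercise arms, a pathway through a marker and a pathway outside it can partly cancel. A non-significant cognitive comparison therefore says little about whether HIIT and CME differ through BDNF or cerebral blood flow, the markers the substudy aims single out.

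At stake is whether one exploratory mechanism analysis is run at all, and a modest upward bias when it is. The condition is also loosely specified. With several cognitive outcomes and no statement on adjustment, the decision to run the analysis could be settled after the results are known.

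**Working it through.** **Inputs.** Enrolment of 110 is from the Study Timeline. Equal allocation is from section D: "Participants will be assigned with equal probability to one of the two exercise intervention arms". No dropout rate is given for the substudy; the parent trial assumes 20% ("with a conservative 20% dropout rate, resulting in 40 evaluable participants/group", section F). No alpha is stated for the cognitive tests; 0.05 is borrowed from the Aim 1 and 2 power text ("between/within group comparisons of the change from baseline with a 0.05 significance level"). The documents state no effect size, SD or power for cognition, so there is no planned power figure to reproduce, and every effect size below is an assumption in SD units of the tested contrast.

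**Sample size.** 60 + 50 = 110. 110/2 = 55 per arm. 55 × 0.80 = 44 per arm. Using the population table's 50 completers of 60 starters instead gives 55 × 50/60 = 45.8, inside the same range.

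**How often the condition fails.** Two-sample t-test, two-sided 0.05, noncentrality d × √(n/2), with 2n − 2 degrees of freedom. For d = 0.5 and n = 44: 0.5 × √22 = 2.345, critical t (86 df) = 1.988, power 64.0%, so the condition fails 36% of the time.

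| Assumed effect (SD) | Fails, 44 per arm | Fails, 55 per arm |
|---|---|---|
| 0.3 | 71% | 66% |
| 0.4 | 54% | 45% |
| 0.5 | 36% | 26% |
| 0.8 | 4% | 1% |

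By the normal approximation, the effect detectable with 80% power is (1.96 + 0.84) × √(2/n): 0.60 SD at 44 per arm and 0.53 SD at 55.

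**What is discarded.** In a simulated single-mediator model (20,000 runs per setting; total effect 0.3 to 0.5 SD; 50% or 100% of it mediated), 18% to 69% of the runs in which both mediation paths were significant failed the cognitive condition. A second assumed case shows why: marker effect 0.6 SD, marker-to-cognition slope 0.4, no direct effect. The total effect is 0.6 × 0.4 = 0.24 SD, which 44 per arm detects only 20% of the time. Both component paths were significant in about 78% of runs, and about 76% of those runs would have been blocked.

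**Bias when the condition is met.** In the first set of simulations the indirect-effect estimate averaged 1.00 times its true value with no condition, and 1.08 to 1.13 times when restricted to runs with a significant cognitive effect. The second case runs somewhat higher, so roughly 8% to 15% is a fair summary.

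**Several outcomes under FDR.** The direction depends on what the plan leaves open.

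- If one outcome must pass p < 0.05/7 (seven outcomes assumed), power at 0.3 to 0.5 SD is 10% to 37% at 44 per arm, so the condition fails 63% to 90% of the time.
- If any of seven outcomes may open the analysis, all share the same true effect, they correlate 0.5 and Benjamini-Hochberg is applied, it fails about 63% of the time at 0.3 SD and 20% at 0.5 SD with 44 per arm. Both are below the single-test figures.

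**The case against.** The strongest reply is that little is lost. The analysis is labelled exploratory. The stated hypothesis of the substudy's exploratory aim is that HIIT improves the markers more than CME, and that is tested by the unconditional group comparison. Other mediation analyses in the same plan carry no stated condition. All of this stands, and it limits the point to the biomarker path analysis.

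Four stronger readings are tempting, and the documents do not support them.

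- A reader might infer that the plan treats a non-significant cognitive result as showing there is nothing to explain. The text says only when a follow-up analysis is run; it makes no such claim.
- A reader might infer that the substudy's cognitive estimate will be inflated. Given significance, the total effect is overestimated on average 1.24-fold at 0.5 SD and 1.84-fold at 0.3 SD (44 per arm). But the main mixed model estimates the total effect in every case, without a filter. The quantity the mediation analysis adds is the indirect effect, where the bias is far smaller. At 0.8 SD even the total-effect inflation is only 1.02-fold.
- A reader might assume that FDR must make the condition harder to meet. As shown in the working, it could go either way.
- A reader might worry about a biased proportion mediated. The plan does not propose to report one.

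It is also fair that the failure rates rest on assumed effects and a borrowed dropout rate, and that mixed models use all available data. That is why the 55-per-arm column and the 0.8 SD row are shown.

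**Conclusion.** The point holds in limited form. The condition has no sound basis as a precondition for mediation, and it is out of line with the estimation approach the same plan adopts for adherence mechanisms. Under a single 0.05 test it would block the analysis in about a quarter to nearly three quarters of trials at assumed effects of 0.3 to 0.5 SD, and rarely at 0.8 SD. The accompanying bias in the indirect effect is modest. Which outcome triggers the analysis, and on which p-value, is undefined. This is a worthwhile correction to one exploratory analysis; it does not threaten any primary result or the biomarker comparisons themselves.

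**What to change.** In the exploratory paragraph of the Cognitive Substudy Statistical Analysis, delete the opening clause that makes the path analysis depend on a significant cognitive effect. State that the path model will be fitted for the named markers (BDNF, and cerebral blood flow at UAB) whatever the cognitive p-value, and that direct, indirect and total effects will be reported with bootstrap 95% confidence intervals as exploratory estimates, matching the approach already planned for adherence mechanisms. Say also that mediation by parent-trial outcomes is unconditional, since its position after the conditional sentence leaves that unclear. Removing the condition also removes the need to define which outcome and which p-value trigger the analysis.

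The cost is a wording change and one more exploratory analysis on data already being collected. The downside is precision: neuroimaging is planned for 50 participants at one site, about 25 per arm, so the interval for the cerebral blood flow pathway will be wide and should be reported as imprecise.

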## COGNITIVE SUBSTUDY AIMS

**AIM 1.** Compare the effects of a 4 month supervised HIIT or CME intervention on (1°) cognitive functioning (i.e., global and domain T scores and diagnoses of cognitive impairment) and (2°) subjective cognitive symptoms. We **hypothesize** that PWH randomized to HIIT will experience greater improvements in objective and subjective cognitive function compared to CME.

**Exploratory Aim 1.** Evaluate the biological mechanisms underlying HIIT and CME. We **hypothesize** that PWH randomized to HIIT will experience greater improvements in putative biomarkers underlying the effect of PA on cognition (blood markers: neurotrophins [e.g., BDNF], growth factors [e.g., VEGF], pro-inflammatory cytokines [e.g., IL-6] and neuroimaging markers: cerebral blood flow, resting state functional connectivity, and brain volume), which a particular focus on BDNF and cerebral blood flow, as they have demonstrated sensitivity to differences between HIIT and CME. Neuroimaging is UAB SITE ONLY.

**AIM 2.** Determine MoA of long-term PA maintenance at 12 months after a 4 month supervised HIIT or CME intervention AND a 3 month coaching or control texting intervention as parent of the parent study design. Distal predictors include sociodemographic (e.g., race, age, sex, education), clinical (e.g., physical health), and intervention factors (i.e., changes in parent R01 physical outcomes [cardiorespiratory fitness], condition [HIIT vs CME], [coaching vs control]). Proximal psychological MoA will be measured in real time with EMA (e.g., self-efficacy, perceived benefits, motivation, social support). We will also examine the extent to which habitual PA in daily life impacts durability of intervention-related cognitive and biomarker improvements from AIM 1.

**Impact:** As older PWH experience more comorbidities and complications, nonpharmacological approaches to improve physical function and alleviate symptoms of the growing population are urgently needed. The HEALTH study will generate scientifically rigorous data on physical function and fatigue responses to exercise, the associated mitochondrial adaptations, and investigate strategies to instill sustained, self-directed exercise behavior. These data will inform the development of scalable, effective exercise recommendations tailored to the unique needs of aging PWH.

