The health benefits of an exercise intervention would be more meaningful if exercise was maintained thereafter. Despite high exercise adherence (92%) during our intervention, most of our participants returned to their pre-intervention sedentary habits. Indeed, <50% reported exercising ≥1 day/week at 12 weeks post-intervention. The marked gains in physical function and exercise self-efficacy (>70% felt “a lot more confident in my ability to exercise”) did not carry over to self-directed exercise. These findings clearly point to a need for *innovative interventions incorporating behavior change strategies*. Regular PA over the lifespan is critical to the health of our nation, particularly among those with multiple chronic health conditions, such as adults aging with HIV. A number of qualitative studies, including our own, have explored attitudes towards PA among diverse PWH and have identified several influencing factors, such as comorbidities, self-efficacy, social support, and accessibility of safe environments for exercise. In focus groups of older PWH in Colorado, participants shared barriers to routine PA, including a lack of social support, loneliness, low exercise self-efficacy (i.e., not sure what to do), and a negative perception of the gym culture. Every group had unprompted discussion about social isolation, or loss of friends or partners due to HIV or other causes, threatening the important social support motivator for exercise. **Many common and unique barriers limit uptake of exercise behaviors among older PWH; empowering this population with tools to overcome these barriers is essential to creating sustainable PA interventions.**

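### The blood-marker model spans baseline, 4 and 12 months without saying how time is coded or which contrast tests Exploratory Aim 1; a linear slope would be a weak test of a 4-month effect

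*Combined protocol and SAP*

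**What the plan says.** In Section F (Cognitive Substudy Statistical Analysis), "The exploratory blood markers will be obtained at baseline, 4- and 12 months". The plan continues: "The group difference of biomarkers will be evaluated using a similar linear mixed regression model". That model contains group, time and their product, "where the group difference on slopes and mean changes will be contrasted". The same sentence also serves the neuroimaging markers, which are measured only at baseline and 4 months and only at UAB.

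The cognitive scores are handled more fully: "In stage 1 (baseline to 4 months), a general linear mixed model with participant ID as random effect", with a site term. A significant interaction there "indicates a significant difference between two trajectories/slopes, i.e., treatment effect". The plan adds: "The group comparison on the mean changes will also be contrasted with t test for effect size". A second-stage model for 4 to 7 months brings in the coaching arm.

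In the Cognitive Substudy Aims, blood markers sit under Exploratory Aim 1, on the biology behind HIIT and CME. Aim 2 asks separately how far everyday activity "impacts durability of intervention-related cognitive and biomarker improvements from AIM 1". Item 20 of the Exploratory Outcome Measures gives the blood-marker outcome as change over 0 to 48 weeks.

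For blood markers the plan does not state whether time is continuous or categorical, what interval the mean change covers, or which of the two contrasts leads. It has no 0–4 month stage and no site term.

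**The concern.** With two visits a slope and a change are the same thing, so the formula suits neuroimaging and stage 1 of the cognitive analysis. Blood markers have three unequally spaced visits, the last about eight months after supervised exercise ends. One straight line through them compares 12-month trends. That is a different question from whether the markers responded differently to the two supervised programmes.

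The distinction matters if a training effect wanes. Section II reports of an earlier exercise study that "<50% reported exercising ≥1 day/week at 12 weeks post-intervention", so waning is at least plausible. The later mediation analysis also uses biomarker changes without naming an interval. If the interval and the leading contrast stay open, the answer to Exploratory Aim 1 could depend on a choice made after the data are seen.

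**Working it through.** The documents state no power, SD or effect size for the blood markers, so there is no figure of theirs to reproduce. The figures below compare the possible contrasts under stated assumptions.

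**Inputs.**
- Visits at 0, 4 and 12 months (16 and 48 weeks have the same 1:3 spacing).
- 110 substudy participants (Study Timeline), so 55 per exercise arm. The parent trial's 20% dropout is carried over: 55 × 0.8 = 44.
- Two-sided tests are the substudy's own rule. The 0.05 level and correlations ρ of 0.5 and 0.7 are carried over from the parent sample-size section.
- Assumed: HIIT advantage d = 0.5 SD at month 4, of which a share f remains at month 12.
- Compound symmetry, which a participant random intercept implies. The plan leaves the structure to BIC, so others follow in step 5.

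**1. Slope weights.** Mean time is 16/3 = 5.33. Deviations are −5.33, −1.33 and +6.67, and their squares sum to 74.67. The weights per month are therefore −0.0714, −0.0179 and +0.0893. Month 4 carries a small negative weight.

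**2. Expected slope difference.** For group differences (0, d, fd) it is d(−0.0179 + 0.0893f). This is zero at f = 0.0179/0.0893 = 0.20, so the expected sign reverses only if less than 20% of the effect remains. With d = 0.5 it is −0.0089 (f = 0), +0.0134 (f = 0.5) and +0.0357 (f = 1) SD per month.

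**3. Power of the slope contrast.** SE = √[(2/44)(1−ρ)/74.67] = 0.0174 at ρ = 0.5 and 0.0135 at ρ = 0.7. Power = Φ(|z|−1.96) + Φ(−|z|−1.96).

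| Share kept at month 12 | z (ρ = 0.5; 0.7) | Power |
|---|---|---|
| 0 | −0.51; −0.66 | 8%; 10% |
| 0.5 | 0.77; 0.99 | 12%; 17% |
| 1 | 2.05; 2.64 | 53%; 75% |

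With the effect fully gone, significant results in favour of CME make up 7–10 percentage points of that power, against 2.5% by chance.

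**4. Power of the month-4 contrast, whatever happens later.**
- Change from baseline: SE = √(2/44) × √[2(1−ρ)] = 0.213; 0.165. z = 2.35; 3.03. Power is 65%; 86%.
- Adjusted for baseline: SE = √(2/44) × √(1−ρ²) = 0.185; 0.152. z = 2.71; 3.28. Power is 77%; 91%.

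**5. Other covariance structures** (44 per arm, d = 0.5, ρ of 0.5 and 0.7 between baseline and month 4):

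| Structure | Slope power, f = 0 | f = 0.5 | f = 1 | Sign reverses below |
|---|---|---|---|---|
| Compound symmetry | 8–10% | 12–17% | 53–75% | 20% kept |
| AR(1) in real time | 5% | 13–17% | 40–52% | 2–5% kept |
| AR(1) by visit | 12–20% | 6–7% | 32–39% | 33–40% kept |

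The month-4 change has 65–86% power in every row. The slope is weaker throughout, but the point at which its sign reverses depends on the structure.

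**The case against.** A reader might infer that the plan's only null is equality of 12-month linear trends, so that a real training effect would be reported as no response or as favouring CME. The documents do not support that.

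- The plan contrasts mean changes as well as slopes. If that contrast covers 0–4 months, it keeps its power. This stands in full; what is missing is the interval and the order of the two contrasts.
- Linear time is inferred from the word slopes. In the cognitive model that word labels the interaction over 0–4 months, where slope and change coincide, and the biomarker model may simply borrow it. This too stands, although the blood-marker visits listed just before run to 12 months.
- The listed outcome runs from 0 to 48 weeks, so a 12-month difference is a legitimate question. It is not obviously the one in Exploratory Aim 1, given that Aim 2 handles durability separately. The cognitive outcome has the same 0–48 week window and is still analysed by stage.
- Fading is not established as the expected pattern. The earlier study's figure concerns exercise frequency; it gives no marker data and no difference between exercise intensities. The protocol itself hypothesises that HIIT participants will keep exercising better.
- Leaving coaching out does not confound the HIIT–CME contrast. Coaching is randomised 1:1 with even allocation across the exercise arms, so the estimate averages over it. A stable site difference likewise cancels from within-person change.

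**Conclusion.** The finding is an under-specified exploratory analysis with a better form readily available; a wrong null has not been shown. If time is linear, the slope is a poor test of a 4-month effect: about 8–10% power if the effect has gone by month 12, 12–17% if it has halved and 53–75% if it is fully kept. The 0–4 month change has about 65–86%, and the baseline-adjusted contrast 77–91%. A reversed sign needs a near-complete fade, below 20% retained under compound symmetry. A halved effect loses power but keeps its sign.

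These figures rest on an assumed 0.5 SD effect, 44 per arm, correlations carried over from the parent trial and an assumed retention. Because the markers are exploratory, this is a low-severity point and a cheap improvement.

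**What to change.** In the Cognitive Substudy Statistical Analysis, separate the blood-marker model from the neuroimaging model and state that:

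- visit is a categorical factor;
- the HIIT–CME difference at month 4, adjusted for the baseline marker and site, is the test of Exploratory Aim 1 (exercise randomisation is site-specific, and site is already in the cognitive model);
- the month-12 difference, which matches the 0–48 week outcome, is a separate durability contrast, with the coaching arm as an optional precision term;
- the biomarker changes used in the mediation analysis cover a named interval.

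This changes wording only and uses the same data. It costs one or two degrees of freedom, and some efficiency if trajectories really are linear to 12 months.
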